3.1 General Design

We propose a pilot proof of principle study to assess and compare the miR fingerprint (or profile) in NAF, serum, and tissue from patients undergoing a lumpectomy or mastectomy for in situ or invasive breast cancer. As this study is a proof of concept there is no power presented. Other than the collection of NAF, treatment will not vary from the standard of care. The collection of all specimen types will be completed within the regularly scheduled operative time period. The surgery will not be prolonged in any way for specimen collection. Forty patients (20 with DCIS, 20 with invasive breast cancer) will be entered into the study. A total of 5 patients will also undergo pharmacokinetic (PK) draws during the time of surgery to assess the baseline oxytocin level. All other subjects enrolled will be enrolled into the “non-PK” cohort. Patients receiving care at the Breast Surgery Department at Columbia who meet criteria will be offered participation in the study. Patients will answer a brief questionnaire preoperatively. At the time of surgery patients will undergo a blood draw as well as collection of NAF (via prior administration of intranasal oxytocin, gentle massage, aspirator, and breast pump from both breasts). The NAF and blood samples will be sent to the pathology lab for analysis of miR profile. At the completion of the case, the breast tissue will be sent to pathology per routine. Once in pathology, 5 paraffin-embedded slices will be created to evaluate for miR profile. Serum, NAF, and tissue will be analyzed for their miR profile.

Once total RNA is extracted from the biological samples it will be processed to fluorescently label the microRNAs species according to the V2-Human microRNA array (Agilent). MicroRNA profiling will be obtained and analyzed using the gene-spring software analysis package. First, expression and cluster analysis will be performed to identify the microRNA that are expressed in our samples and to classify them accordingly to their expression. Then, the predicted targets of the over/down-regulated microRNAs will be identified using target prediction bioinformatics tools (TargetScan, Miranda and Pictarvert). Finally, statistical studies between over/under-represented microRNAs will be performed.

3.2 Primary Study Endpoints

The primary endpoint is feasible miR analysis of NAF as well as serum and tissue collected from study participants.

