8.3.2	EC/IRB Notification by Investigator	15
8.3.3	FDA Notification by Sponsor	16
SERIOUS ADVERSE EVENTS NOT CONSTITUTING UNANTICIPATED PROBLEMS ARE TO BE REPORTED TO THE HICCC DSMC. REPORTING SHOULD OCCUR WITHIN 24 HOURS OF KNOWLEDGE OF THE SAE OCCURRING AT OUR INSTITUTION OR AFFILIATE SITES.		17
8.4	UNBLINDING PROCEDURES	17
8.5	STOPPING RULES.....	17
8.6	MEDICAL MONITORING.....	17
8.6.1	Internal Data and Safety Monitoring Board	17
8.6.2	Independent Data and Safety Monitoring Committee	18
9	DATA HANDLING AND RECORD KEEPING	17
9.1	CONFIDENTIALITY.....	17
9.2	SOURCE DOCUMENTS.....	18
9.3	CASE REPORT FORMS.....	18
9.4	RECORDS RETENTION	18
10	STUDY MONITORING, AUDITING, AND INSPECTING	18
10.1	STUDY MONITORING PLAN	18
10.2	AUDITING AND INSPECTING.....	19
11	ETHICAL CONSIDERATIONS	19
12	STUDY FINANCES	19
12.1	FUNDING SOURCE	19
12.2	CONFLICT OF INTEREST	19
12.3	SUBJECT STIPENDS OR PAYMENTS	20
13	PUBLICATION PLAN	20

CONFIDENTIAL

This material is the property of [name]. Do not disclose or use except as authorized in writing by the study sponsor

List of Abbreviations

DCIS: ductal carcinoma in situ

IM: intramuscular

IV: intravenous

miR: microRNA

NAF: nipple aspirate fluid

PK: pharmacokinetic

SQ: subcutaneous

CONFIDENTIAL

This material is the property of [name]. Do not disclose or use except as authorized in writing by the study sponsor

Study Summary

Title	INTRANASAL OXYTOCIN USE IN IDENTIFYING THE MICRO-RNA FINGERPRINT IN NAF, SERUM, AND TISSUE IN PATIENTS WITH DCIS OR INVASIVE BREAST CANCER
Short Title	Oxytocin, microRNA and breast cancer
Protocol Number	IRB-AAAL5203
Phase	Pilot
Methodology	Pilot proof of principle study
Study Duration	1 year
Study Center(s)	Columbia University Medical Center
Objectives	To determine the feasibility of assessing miR profiles in NAF, serum and tissue of women diagnosed with DCIS or invasive breast cancer
Number of Subjects	40
Diagnosis and Main Inclusion Criteria	Patients with DCIS or invasive breast cancer scheduled for breast surgery at Columbia Medical Center
Study Product, Dose, Route, Regimen	Oxytocin (Syntocinon Spray), 4 IU (1 spray) per nostril, intranasal route, prior to nipple aspirate fluid collection
Duration of administration	Once before NAF is collected
Reference therapy	None

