3.3 Secondary Study Endpoints

The secondary endpoint is sufficient NAF volumes following the administration of oxytocin.

CONFIDENTIAL

This material is the property of [name]. Do not disclose or use except as authorized in writing by the study sponsor

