7.1 Sample Size Consideration

Contralateral breast without disease will serve as the control. In a sample of 40 patients with unilateral disease, we expect 60% of the patients to show significantly altered expression of miRNAs in the diseased breast as compared to the breast without disease for the test to be of clinical relevance. Ideally a detectable difference would be the difference between a null hypothesis of 0% and an alternative of 60% or a second alternative of 35%. Since this study is the first of its kind, we will consider the test to be not clinically relevant if less than 35% of patients show significantly altered expression miRNA in the diseased breast as compared to the breast without disease.

Using a two sample z-test, type I error of 0.05, and a two-sided significance level, a sample size of 40 will have greater than 80% power to detect a difference between a null hypothesis of 35% and an alternative hypothesis of 60%.

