7.2 Statistical Methods

The primary analysis will be conducted to determine the presence and expression levels of 800 miRNA's among DCIS and invasive breast cancer patients. Based on the resulting profiles, we will determine whether or not its expression for each miRNA from the tumor side differs from that of the normal side.

We will interrogate 800 miRNAs. The vast majority will not be expressed in any sample. A minority will be measurable/detectable in some samples and a smaller minority will be detectable in all samples.

The presence of miRNA can be as follows:

- a. Present in tumor and absent in normal
- b. Present in normal and absent in tumor
- c. Present at high level in tumor and low level in normal
- d. Present at high level in normal side and low level in tumor.

Of these a and c are most important and relevant for our analysis. If even a single miRNA is absent in tumor and present in 30% of cancers or if there is at least one miRNA out of these 800 that is present at low levels in all "normals" and high levels in 30% of tumors that would be a "success". We will dichotomize to low and high levels of miRNA to calculate frequencies and the associated risk estimates and 95% confidence intervals. The comparison of proportions will be performed using two-sample z-tests.

CONFIDENTIAL

This material is the property of [name]. Do not disclose or use except as authorized in writing by the study sponsor

7.3 *Subject Population(s) for Analysis*

Patients diagnosed with DCIS or invasive breast cancer.

8 Safety and Adverse Events

8.1 *Definitions*

Adverse Event

An ***adverse event*** (AE) is any symptom, sign, illness or experience that develops or worsens in severity during the course of the study. Intercurrent illnesses or injuries should be regarded as adverse events. Abnormal results of diagnostic procedures are considered to be adverse events if the abnormality:

- results in study withdrawal
- is associated with a serious adverse event
- is associated with clinical signs or symptoms
- leads to additional treatment or to further diagnostic tests
- is considered by the investigator to be of clinical significance

Serious Adverse Event

Adverse events are classified as serious or non-serious. A ***serious adverse event*** is any AE that is:

- fatal
- life-threatening
- requires or prolongs hospital stay
- results in persistent or significant disability or incapacity
- a congenital anomaly or birth defect
- an important medical event

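### The power stated in 7.1 does not belong to the two-sample z-test named there, and Section 7 plans no estimate of the feasibility and NAF-volume endpoints

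*Combined protocol and SAP*

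**What the plan says.** **Endpoints.** The Study Summary gives the objective as "To determine the feasibility of assessing miR profiles in NAF, serum and tissue of women diagnosed with DCIS or invasive breast cancer". Section 3.2 follows it: "The primary endpoint is feasible miR analysis of NAF as well as serum and tissue collected from study participants". Section 3.3 adds: "The secondary endpoint is sufficient NAF volumes following the administration of oxytocin". Section 2 expects bilateral NAF of adequate volume from 77% of participants, a figure cited for women at increased risk, and expects serum and tissue from every patient. It also reports that the initial trial, without oxytocin, obtained NAF from 13 of 40 patients and analysed 8.

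**Analysis.** Section 7.2 opens with "The primary analysis will be conducted to determine the presence and expression levels of 800" miRNAs, then compares the tumor side with the normal side. It declares success on a 30% expression rule whose first limb begins "If even a single miRNA is absent in tumor and present in 30% of cancers". It names two-sample z-tests for comparing proportions. Section 7.1 treats the result as not clinically relevant if fewer than 35% of patients show "significantly altered expression of miRNAs in the diseased breast as compared to the breast without disease".

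**Power.** Section 7.1 reads "Using a two sample z-test, type I error of 0.05, and a two-sided significance level, a sample size of 40" and claims more than 80% power for 35% against 60%. Section 3.1 says "As this study is a proof of concept there is no power presented". The Study Summary names a different approach: a binomial test against a normative reference population, with a Benjamini-Hochberg procedure.

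**The concern.** There are two separate problems.

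First, the declared endpoints and the declared primary analysis are different quantities. Whether an analysable profile can be obtained from a patient is a yield question. Whether a miRNA differs between the two breasts is an expression question. Section 7 covers only the second. The extension with oxytocin exists because NAF yield was poor in the initial trial, so the yield result is the one readers will want. As written, nothing in the analysis plan says how it will be estimated, over which patients, or what makes a specimen analysable or a volume sufficient.

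Second, 7.1 gives a power figure and names a test, and the two do not go together. Anyone who carries out the named test, or relies on the stated power for it, is misinformed. The test also assumes two independent groups, whereas 7.1 makes each patient's unaffected breast her control.

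**Working it through.** **Inputs.** From 7.1: p0 = 0.35, p1 = 0.60, two-sided α = 0.05 (z = 1.96), N = 40, contralateral breast as control. From 3.1: 20 DCIS and 20 invasive patients. From Section 2: 77% expected bilateral NAF; 13/40 and 8 in the initial trial.

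**1. The test named in 7.1.** For a pooled two-sample z-test with n per group and mean proportion p̄ = 0.475:

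power = Φ{[0.25 − 1.96·√(2·p̄(1−p̄)/n)] / √[(0.35·0.65 + 0.60·0.40)/n]}

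- n = 40 per group: (0.25 − 1.96 × 0.1117)/0.1081 = 0.288, so power is 61.3%.
- n = 20 per group (the only two patient groups in the protocol): 34.9%.
- 80% power needs 62 per group (80.4%).
- Other forms at 40 per group: unpooled 63.8%, arcsine 61.9%, one-sided pooled 73.0%, one-sided unpooled 74.8%.

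None of these reaches 80%, so the stated figure is not reproduced.

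**2. A reading that does reproduce it.** Test one proportion against a fixed 35%:

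power = Φ{[0.25 − 1.96·√(0.35·0.65/n)] / √(0.60·0.40/n)}

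- n = 40: (0.25 − 1.96 × 0.0754)/0.0775 = 1.319, so power is 90.6%.
- Exact binomial, upper tail at most 0.025: reject at 21 or more of 40 (tail 0.0173); power 87.0%.

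The claim of more than 80% is true for this test.

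**3. Fewer evaluable patients.** 7.1 makes no allowance for patients without usable specimens and does not say which specimen the comparison uses. Disease is unilateral (4.1), serum has no side, and the tissue planned is from the on-study surgery (6.3). NAF is the only specimen planned from both breasts, so the comparison appears to need bilateral NAF. That is an inference. At 77%, 40 × 0.77 = 30.8, or about 31 pairs. Averaging one-sample power over a binomial number of evaluable patients gives:

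| Bilateral yield | Normal approximation | Exact |
|---|---|---|
| 60% (assumed) | 72% | 62% |
| 77% (Section 2) | 82% | 76% |
| 90% (assumed) | 87% | 83% |

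Exact power moves in steps: 71%, 78% and 73% at 30, 31 and 32 pairs.

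**4. If a paired comparison of 35% and 60% was meant.** McNemar power depends on the discordance π, which the protocol does not give: Φ{[0.25·√40 − 1.96·√π] / √(π − 0.25²)}. Assuming π = 0.25 gives 92%; π = 0.53 gives 59%. It can fall on either side of 80%.

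**5. Endpoints against analyses.**

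| Stated question | Estimate planned in Section 7 | Decision rule |
|---|---|---|
| Feasible analysis of NAF, serum, tissue (3.2) | none | none |
| Sufficient NAF volume (3.3) | none | none |
| Tumor versus normal expression (7.1, 7.2) | yes, called primary | 35% of patients; 30% of tumors |

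**6. What the choice of denominator does.** With exact 95% intervals, the initial trial's 8 analysed patients are 8/40 = 20% (9% to 36%) of those enrolled, or 8/13 = 62% (32% to 86%) of those with NAF. NAF collection was 13/40 = 32.5% (19% to 49%).

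**7. Precision available at 40.** 20/40 gives 34% to 66%, the widest case at about ±16 points; 31/40 gives 62% to 89%; 40/40 gives 91% to 100%.

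**The case against.** The strongest reply on power is that 7.1 contains a mislabelled test and not a failed design. A null of 35% and an alternative of 60% describe one proportion against a fixed value, and the Study Summary does name a binomial test. This stands. A reader might infer from the 61% that 40 patients are too few. The documents do not support that: there are no two groups of 40 in this trial, and the one-sample reading clears 80% with 40 evaluable patients.

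On the endpoints, the reply is that Section 2 supplies per-participant benchmarks for all three specimen types and reports the earlier yield openly, with 40 as the denominator for NAF collection. That also stands, so it would be wrong to say that the protocol has no yardstick. But these are expectations. Adequate volume is undefined, and no estimate or comparison is tied to the figures. Nothing suggests that the investigators would pick the kinder denominator; the point is only that Section 7 leaves it open.

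A reader might also infer that 7.2's success rule can be met or missed whatever the NAF yield. That goes too far. If bilateral NAF is the only two-sided specimen, the expression comparison depends on yield. It still does not measure it.

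Finally, this is a single-centre pilot. Counts with clear denominators would meet most of the need, and a numeric go/no-go threshold is a matter of choice.

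**Conclusion.** Both parts hold, within limits.

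1. The more-than-80% power in 7.1 does not belong to the two-sample z-test, which gives 61% at 40 per group and 35% at 20 per group and does not fit a design with a within-patient control. The figure is right for a one-sample test against 35% (91% normal approximation, 87% exact at 40 evaluable). The named test needs correcting; the sample size has not been shown to be inadequate. If bilateral NAF is required, power at the 77% yield is about 82% by normal approximation and 76% exact, so the claim survives narrowly on one calculation and not on the other. That rests on the inference about specimens and on a yield cited for women at increased risk. Section 3.1's statement that no power is given conflicts with 7.1 in any case.

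2. The primary and secondary endpoints have no planned estimate, and the analysis labelled primary answers a different question.

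The data would remain usable, but both points should be corrected before assay results are seen, because definitions set afterwards cannot be shown to be independent of the results.

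**What to change.** **Section 7.1.** Name a one-sample exact binomial test of the proportion of patients against 35%. Define per patient what counts as significantly altered, applying the Benjamini-Hochberg procedure already named in the Study Summary across the 800 miRNAs. State power as 87% exact (91% normal approximation) at 40 evaluable. If bilateral NAF is required, say so and give the range: about 76% exact (82%) at 77% yield, and 62% to 83% exact (72% to 87%) for assumed yields of 60% to 90%. Reconcile this with Section 3.1.

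**Section 7.2.** Replace the two-sample z-tests with a paired comparison of the tumor and contralateral sides, such as McNemar's test. Reconcile the Study Summary's normative reference population with the contralateral control. Label expression secondary, or an explicit co-primary.

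**Primary and secondary analyses.** Before assay results are seen, define an analysable profile for each specimen type and a sufficient NAF volume. As the primary analysis, report the proportion of all 40 enrolled with an analysable profile, separately for NAF (any and bilateral), serum and tissue. Give exact 95% intervals and count missing specimens as failures. Report sufficient NAF volume the same way as the secondary analysis. Set the results beside Section 2's expectations and the initial trial's 13/40 and 8/40, descriptively only. A numeric go/no-go threshold is optional.

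**Cost.** Protocol wording and one table; no new samples or visits. The stated power becomes less favourable once yield is allowed for, the feasibility figure is lower than a rate among specimens collected, and expression may lose its sole primary label.

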3.3 Secondary Study Endpoints

The secondary endpoint is sufficient NAF volumes following the administration of oxytocin.

CONFIDENTIAL

This material is the property of [name]. Do not disclose or use except as authorized in writing by the study sponsor

3.4 Primary Safety Endpoints

The primary safety endpoints are anaphylactic reactions or water intoxication secondary to intranasal oxytocin. Refer to 1.5 for complete list of side effects.

4 Subject Selection and Withdrawal

4.1 Inclusion Criteria

Patients meeting the following criteria may be included in the study:

- All female patients with DCIS or invasive breast cancer who are scheduled for a lumpectomy or mastectomy and are receiving surgical care from the Breast Surgery Department at Columbia Medical Center.
- Patients diagnosed with unilateral DCIS or invasive breast cancer

4.2 Exclusion Criteria

Patients meeting the following criteria will be excluded from the study:

- Patients not receiving breast surgery care from the Department of Breast Surgery at Columbia Medical Center.
- Pregnant patients are to be excluded given the risk associated with oxytocin.
- Male patients
- Patients with a prior breast cancer diagnosis
- Patients who have had an adverse reaction to oxytocin

4.3 Subject Recruitment and Screening

Patients with unilateral DCIS or invasive breast cancer who are scheduled for a lumpectomy or mastectomy will be offered participation in this study. A negative pregnancy test is required for all women with child-bearing potential. Post-menopausal women (i.e., women who have not menstruated for at least 1 year) and women who have undergone hysterectomy or bilateral oophorectomy will not need to undergo a pregnancy test. All women of childbearing potential will be tested for pregnancy prior to enrollment. All participants will receive their care at Columbia Presbyterian in the Breast Surgery Department.

4.4 Early Withdrawal of Subjects

Subjects may withdraw at any time during the study.

4.4.1 When and How to Withdraw Subjects

Subjects may withdraw from the study at any time for any reason, and can do so by contacting the study coordinator by phone or e-mail.

4.4.2 Data Collection and Follow-up for Withdrawn Subjects

Withdrawn subjects may continue to follow-up at Columbia Presbyterian, but are not obligated to donate NAF, serum or tissue samples.

CONFIDENTIAL

This material is the property of [name]. Do not disclose or use except as authorized in writing by the study sponsor

5 Study Drug

5.1 Description

Oxytocin is a natural neuropeptide that is synthesized in the hypothalamus and released by the posterior pituitary. It is most commonly known in the United States for its role in promoting uterine contractions during labor. In addition, the oxytocin pathway can also be triggered by suckling, which causes contraction of mammary myoepithelial cells and subsequent milk ejection.¹³ Recent studies demonstrate intranasal oxytocin's utility in enhancing the yield of nipple aspirate fluid (NAF) among healthy, non-lactating female patients as well as those at high risk for breast cancer. This capability is crucial for the analysis of various markers associated with breast disease and cancer such as proteins, methylated DNA and miRs.^{14,15,16}

Intranasal oxytocin ("Syntocinon Spray") had been approved by the United States Food and Drug Administration (FDA) prior to 1982 for initial milk letdown, but was withdrawn from the market in 1995 by its manufacturer, Novartis, for financial reasons.¹⁷ Oxytocin now exists solely as the intravenous (IV) and intramuscular (IM) forms in the US. It is marketed under the brand name "Pitocin" for induction, stimulation or reinforcement of labor; adjunctive therapy in abortion; promotion of uterine contractions during the third stage of labor; and control of postpartum bleeding.¹⁸ The nasal spray remains available outside of the US.

5.2 Treatment Regimen

The Principal Investigator will administer one spray of intranasal oxytocin, or 4 IU, into each nostril approximately 15-30 minutes before NAF collection. Prior to collection, the nipples will be scrubbed with alcohol swabs to eliminate keratin plugs, breasts will be massaged by the MD investigator for approximately 2 minutes, but no more than approximately 7 minutes. An aspirator will be applied to each breast, and fluid will be collected into capillary tubes. NAF samples will be acquired from study subjects by the MD investigator in the operating room while under anesthesia before the opening incision. The duration of time required to obtain NAF samples will be documented.

5.3 Method for Assigning Subjects to Treatment Groups

All subjects will receive the same treatment.

5.4 Preparation and Administration of Study Drug

Intranasal spray. One spray or 4 IU of oxytocin will be administered into each nostril of each patient approximately 15-30 minutes before NAF collection. Study drug will be administered by the Principal Investigator.

5.5 Subject Compliance Monitoring

The principal investigator will administer the intranasal oxytocin, therefore assuring compliance. Proper documentation will be obtained.

5.6 Prior and Concomitant Therapy

N/A

CONFIDENTIAL

This material is the property of [name]. Do not disclose or use except as authorized in writing by the study sponsor

5.7 *Packaging*

Intranasal oxytocin is packaged into spray containers by the manufacturer (Novartis).

5.8 *Blinding of Study Drug*

N/A. All patients enrolled in the study will receive intranasal oxytocin.

5.9 *Receiving, Storage, Dispensing and Return*

5.9.1 *Receipt of Drug Supplies*

Upon receipt of the of the study treatment supplies, an inventory must be performed and a drug receipt documented by the appropriate research pharmacy personnel accepting the shipment. It is important that the designated study staff counts and verifies that the shipment contains all the items noted in the shipment inventory. Any damaged or unusable study drug in a given shipment (active drug or comparator) will be documented in the study files.

5.9.2 *Storage*

The drug must be refrigerated at 35.6 – 46.4 degrees Fahrenheit, and may be used up to 1 month after opening.

5.9.3 *Dispensing of Study Drug*

The drug will be stored at and dispensed by at the research pharmacy.

5.9.4 *Return or Destruction of Study Drug*

Empty/used oxytocin spray containers will be returned to the research pharmacy. At the completion of the study, there will be a final reconciliation of drug shipped, drug consumed, and drug remaining. This reconciliation will be logged on the drug reconciliation form, signed and dated. Any discrepancies noted will be investigated, resolved, and documented prior to return or destruction of unused study drug. Drug destroyed on site will be documented in the study files.

6 *Study Procedures*

6.1 *Visit 1*

The collection of all specimen types will be completed within the regularly scheduled operative time period. The surgery will not be prolonged in any way for specimen collection. Patients will answer a brief questionnaire preoperatively, after the subject has consented to the trial and prior to administration of oxytocin. Blood pressure will be recorded prior to oxytocin administration and 5 minutes post-administration of oxytocin.

All patients will undergo a blood draw as well as collection of NAF (via prior administration of intranasal oxytocin, gentle massage, aspirator, and breast pump from both breasts). All biological samples will be collected by a qualified clinician. The NAF and blood samples will be sent to the pathology lab for analysis of miR profile. At the completion of the case, the breast tissue will be sent to pathology per routine. Once in pathology, 5 paraffin-embedded slices will be created to evaluate for miR profile. Serum, NAF, and tissue will be analyzed for their miR profile.

CONFIDENTIAL

This material is the property of [name]. Do not disclose or use except as authorized in writing by the study sponsor

Five patients who are participating in the PK cohort of the trial will also undergo a PK blood draw at the time of surgery prior to oxytocin administration. This will be used to assess the baseline oxytocin level and will be done in conjunction with the pre-oxytocin blood draw to assess miR. These patients will have a second blood draw approximately 30 minutes after the administration of oxytocin to assess oxytocin levels in comparison to the baseline. All blood draws will be done by a qualified clinician.

Once total RNA is extracted from the biological samples it will be processed to fluorescently label the microRNAs species according to the V2-Human microRNA array (Agilent). MicroRNA profiling will be obtained and analyzed using the gene-spring software analysis package. First, expression and cluster analysis will be performed to identify the microRNA that are expressed in our samples and to classify them accordingly to their expression. Then, the predicted targets of the over/down-regulated microRNAs will be identified using target prediction bioinformatics tools (TargetScan, Miranda and Pictarvert). Finally, statistical studies between over/under-represented microRNAs will be performed.

